2. SYNOPSIS

Name of Sponsor/Company: Marinus Pharmaceuticals, Inc.	
Protocol Number: 1042-0604	Phase of Development: III
Title of the Protocol: A follow-on, two-year open-label extension study of ganaxolone as add-on therapy in adult subjects with drug-resistant partial-onset seizures	
Primary Objectives: To assess the safety and tolerability of adjunctive ganaxolone during a two-year open-label treatment in adult subjects with drug-resistant partial-onset seizures	
Secondary Objectives: To assess efficacy of adjunctive ganaxolone during a two-year open-label treatment in adult subjects with drug-resistant partial-onset seizures	
Study Design and Methodology: Subjects who successfully completed Study 1042-0603 and meet inclusion/exclusion criteria are eligible to enter Study 1042-0604 and continue open-label adjunctive treatment with ganaxolone capsules in the dose range of 900 - 1800 mg daily.	
Study Population and Main Criteria for Inclusion/Exclusion: Adults with drug-resistant partial onset seizures currently taking 1-3 prescribed AEDs who completed all scheduled clinical study visits in Study 1042-0603, were compliant, derived benefit from open-label ganaxolone and did not experience any serious or medically important adverse event judged probably or definitely due to ganaxolone.	
Number of Subjects: A maximum of approximately 350 subjects may enter this protocol, after satisfactorily completing Study 1042-0603.	
Test Product, Dose and Mode of Administration: Ganaxolone 225 mg capsules administered in BID in the dose range of 900 to 1800 mg/day.	
Duration of Treatment: Up to 104 weeks treatment on the maintenance dose with an additional 2 weeks of dose de-escalation.	
Reference Therapy, Dose and Mode of Administration: None	
Safety Criteria for Evaluation: Adverse Events, vital signs, safety laboratory assessments, ECGs	

2.1 Table 1: Schedule of Events

WEEK	0	17	34	52	69	86	104 (Study completion/ET)	106 (Post-Taper Safety Follow-Up)	Unscheduled Visit ⁴
Visit Windows (Weeks)	±2	±2	±2	±2	±2	±2	±2	±2	
VISIT	V1 / Study 1042-0603 Visit 10	V2	V3	V4	V5	V6	V7	V8	
Informed consent	X								
Demographics & Medical HX ¹	X								
Inclusion/Exclusion criteria	X								
Concomitant AEDs ² Review	X	X	X	X	X	X	X	X	X
Safety Assessments									
Physical examination	X ³			X			X		
Physical brief exam		X	X		X	X		X	
Vital signs	X ³	X	X	X	X	X	X	X	X
Neurological examination	X ³			X			X		
Neurological brief exam		X	X		X	X		X	
ECG (12 lead) ⁵	X ³			X			X		
Safety Labs	X ³	X	X	X	X	X	X	X	X
Urine Pregnancy test (WCBP)	X ³	X	X	X	X	X	X	X	
Columbia Suicide Scale (C-SSRS)	X ³	X	X	X	X	X	X	X	
Review safety and record AEs	X ³	X	X	X	X	X	X	X	X
Efficacy Assessments									
Subject Calendar Review	X ³	X	X	X	X	X	X	X	
Clinician's Global Impression of Improvement	X ³	X	X	X	X	X	X		
Patient / Caregiver Global Impression of Improvement	X ³	X	X	X	X	X	X		
Study Medication									
Dispense study medication	X	X	X	X	X	X	X		
Study medication compliance check		X	X	X	X	X	X	X	
Visit Windows (Weeks)	±2	±2	±2	±2	±2	±2	±2	±2	

¹ Any Adverse Event that occurred in 1042-0603 which is not resolved at the time of enrollment into 1042-0604 or is deemed significant by the Principal Investigator is to be captured in the subject's 1042-0604 medical history

² Concomitant AEDs and their dose and VNS settings should be stable for 1 month prior to entry into the study

³ These procedures will be captured in Study 1042-0603 database as part of the Visit 10

⁴ Check Vital Signs at all unscheduled visits. Other procedures performed as needed

⁵ ECGs will be done locally

ET = Early Term; AED = antiepileptic drug; AEs = adverse events; ECG = electrocardiogram; WCBP = women; C-SSRS = Columbia-Suicide Severity Rating Scale

TABLE OF CONTENTS

1.	SIGNATURE PAGE	2
2.	SYNOPSIS	3
2.1	Table 1: Schedule of Events	4
3.	LIST OF ACRONYMS, ABBREVIATIONS, AND DEFINITIONS OF TERMS	7
4.	ETHICS	9
4.1	Independent Ethics Committee (IEC) or Institutional Review Board (IRB)	9
4.2	Ethical Conduct of Study	9
4.3	Subject Information and Consent	9
5.	INVESTIGATORS AND STUDY ADMINISTRATIVE STRUCTURE	10
6.	INTRODUCTION	11
7.	STUDY OBJECTIVES	14
7.1	Primary	14
7.2	Secondary	14
8.	INVESTIGATIONAL PLAN	15
8.1	Overall Study Design and Plan	15
8.2	Discussion of Study Design	15
8.3	Selection of Study Population	16
8.3.1	Number of Subjects:	16
8.3.2	Inclusion Criteria	16

3. LIST OF ACRONYMS, ABBREVIATIONS, AND DEFINITIONS OF TERMS

Term	Definition
3 α ,5 α -P	3 α -hydroxy-5 α -pregnan-20-one; allopregnanolone
AE	adverse event
AE CRF	adverse event case report form
AED	antiepileptic drug
ALT	alanine transferase (SGPT)
ARS	acute repetitive seizures
AST	aspartate transferase (SGOT)
ANCOVA	analysis of covariance
BID	bis in die; two times per day
CFR	Code of Federal Regulations
°C	degrees centigrade
CGI-I	Clinician's Global Impression of Improvement
CNS	central nervous system
CPS	complex partial seizures
CRF	case report form
C-SSRS	Columbia-Suicide Severity Rating Scale
CT	computed tomography
DB	double-blind
DDI	drug-drug interaction
ECG, EKG	electrocardiogram
EEG	electroencephalogram
ET	Early Termination
°F	degrees Fahrenheit
FAP	full analysis population
FDA	Food and Drug Administration
POS	Partial-onset seizure
FS	Focal seizure
FPFV	first patient, first visit
GABA _A	γ -aminobutyric acid _A
GCP	Good Clinical Practice
GTCS	generalized tonic-clonic seizure
Hz	Hertz
ICF	informed consent form
ICH	International Conference on Harmonisation
IEC	Independent Ethics Committee
IND	Investigational New Drug
ILAE	International League Against Epilepsy
IPIN	Investigational Product Identification Number
IRB	Institutional Review Board
ITT	intent-to-treat
IWRS	interactive web response system
kg	kilogram
LOCF	last observation carried forward
LPLV	last patient, last visit
m	meter
MedDRA	Medical Dictionary for Regulatory Activities
mg	milligram

Term	Definition
mg/d	milligram per day
min	minutes
mL	millilitre
MRI	magnetic resonance imaging
MTD	maximum tolerated dose
n	number of subjects
OL	open-label
OLE	open-label extension
oz	ounces
PCGI-I	Patient/Caregiver Global Impression of Improvement
PK	pharmacokinetics
POS	partial-onset seizure
PTZ	pentylenetetrazol
PP	per-protocol
SAE	serious adverse event
SAE CRF	serious adverse event case report form
SOC	system organ class
SP	safety population
SPS	simple partial seizure
t.i.d.	three times daily
T _{max}	time to maximum concentration
ULN	upper limits of normal
USA	United States of America
VNS	vagal nerve stimulator
WCBP	women of child bearing potential

4. ETHICS

4.1 Independent Ethics Committee (IEC) or Institutional Review Board (IRB)

This study will be conducted in compliance with current Good Clinical Practices (GCP) and Title 21 Part 56 of the United States of America (USA) Code of Federal Regulations (CFR) relating to IRBs and the International Conference on Harmonisation (ICH) E6 guidelines for Good Clinical Practice.

4.2 Ethical Conduct of Study

The study will be conducted in accordance with GCP as described in the USA Food and Drug Administration (FDA) CFR (21 CFR § 50, 56, 312), and the International Conference on Harmonisation (ICH) and the ethical principles of the Declaration of Helsinki.

4.3 Subject Information and Consent

This study will be conducted in compliance with Title 21 Part 50 of the USA CFR and ICH E6(R1) (Section 4.8) pertaining to informed consent. At the first visit, prior to initiation of any study-related procedures, subject will give their written consent to the study after having been informed about the nature and purpose of the study, conditions for study participation/termination, and potential risks and benefits.

5. INVESTIGATORS AND STUDY ADMINISTRATIVE STRUCTURE

This will be a multi-center study with approximately 58 investigational sites in the USA, the Russian Federation (Russia), Australia, Bulgaria, Germany and Poland with approximately 6 subjects enrolled at each site. Duration of subject participation is 106 weeks.

6. INTRODUCTION

Approximately 2 million people in the United States of America (USA) have epilepsy. As many as 30% of epilepsy subjects may not be well controlled on treatment with a single or multiple existing antiepileptic drugs (AEDs; [French et al., 2004](#)). The approach of adding on an experimental AED to an existing non-optimal therapeutic regimen has proven to be a useful technique for demonstrating efficacy of novel compounds. The present study will evaluate the safety, tolerability and efficacy in a second year of open-label treatment with ganaxolone when used as an add-on therapy in adult subjects with drug-resistant partial-onset (focal) seizures.

Ganaxolone is the 3 β -methylated synthetic analog of allopregnanolone, which is synthesized *in vivo* when progesterone undergoes 5 α -reduction and loses all progestational activity. Ganaxolone is a positive allosteric modulator of γ -aminobutyric acid A (GABA_A) receptors with potency and efficacy comparable to its endogenous analog allopregnanolone ([Carter et al., 1997](#)). As with allopregnanolone, ganaxolone potentiation of the GABA_A receptor occurs at a site distinct from the benzodiazepine site. Ganaxolone has protective activity in diverse rodent seizure models, including clonic seizures induced by pentylenetetrazol (PTZ) and bicuculline, limbic seizures in the 6 Hz model, and amygdala kindled seizures ([Carter et al., 1997](#); [Kaminski et al., 2004](#); [Reddy et al., 2004](#)). Unlike allopregnanolone, ganaxolone cannot be converted to an active steroid; it is currently under study for treatment of chronic neurologic and psychiatric conditions such as adult and pediatric epilepsy, Posttraumatic Stress Disorder and behaviors in Fragile X Syndrome. Human trials indicate that ganaxolone is well tolerated and that it may be efficacious in the treatment of diverse forms of epilepsy in children and adults ([Bialer et al. 2010](#)).

As of May 31, 2013, 986 subjects have received and completed treatment with ganaxolone in 35 studies, ranging in duration from 1 day to more than 2 years. Two hundred and eighty-nine subjects received ganaxolone in Phase 1 studies, including 22 subjects in Study 1042-0404 which was an open-label, ascending multiple-dose safety and tolerability study of 1200, 1600 and 2000 mg/day.

Subjects in Study 1042-0404 were maintained at each dose level for 3-5 days; the doses were safe and generally well-tolerated. Pharmacokinetics were assessed at steady state after each dose level. Results showed that both Cmax and levels increased with increasing dose over the range of 600 to 1000 mg BID under fed conditions, though not in proportion to increases in dose. The incidence of adverse events (AEs) was dose-related and most AEs were classified as mild and possibly related to study drug. The most common AEs affecting more than 20% of subjects (n, %) were somnolence (19, 86%), euphoric mood (13, 59%), nausea (8, 36%), headache (6, 27%), and tremor, flatulence and muscle spasms (each 5, 23%). There were no clinically significant findings for laboratory safety values, vital signs or ECG data. There were no positive findings on the Columbia-Suicide Severity Rating Scale (C-SSRS) during the study.

In Phase 2 adult trials in the ganaxolone program, 697 adults received ganaxolone in 9 studies, 6 of which were in epilepsy. To date, the largest placebo-controlled completed study (N=147) of ganaxolone in epilepsy was 10-week, double-blind Study 1042-0600 followed by an open-label extension of up to two years duration. Study 1042-0600 showed ganaxolone (500 mg tid) adjunctive therapy significantly reduced partial onset seizures, with or without secondary generalizations, compared to placebo (p= 0.014). Ganaxolone-treated subjects experienced a median decrease of 26% (17.6% mean) compared to a 10.2% (+2.0% mean) decrease in placebo.

Most of the adverse events reported in the clinical development program were mild or moderate in severity, dose-related, and resolved upon treatment discontinuation. Adult and pediatric subjects in open label extension studies to the epilepsy trials have been dosed with ganaxolone for >2 years with no new adverse events reported as compared to the controlled trials. Three deaths have been reported in the program, none related to ganaxolone.

Adverse events reported from Study 1042-0600 in at least 5% of subjects and >1.5 times more frequent in the ganaxolone group than the placebo group were dizziness (16.3 v. 8.3%), fatigue (16.3 v. 8.3%) and somnolence (13.3 v. 2.0%). The discontinuation rates due to adverse events between the ganaxolone and placebo groups in Study 1042-0600 were comparable, 7.1% and 6.1% respectively.

In Study 1042-0600 and in the ganaxolone development program overall, no clinically significant trends in changes from baseline electrocardiogram (ECG) recordings, vital signs, or physical or neurological examinations have been noted in the clinical studies, and no mean changes from baseline in clinical labs have been identified. Transient increases in LFTs ($>3\times\text{ULN}$) have been noted in less than 1% of subjects treated with ganaxolone. Serious adverse events (SAEs) reported in the ganaxolone epilepsy trials were considered by a Scientific Advisory Board to be usual for the population without any pattern attributable to ganaxolone. Profiles of the most frequently reported AEs have been consistent with the predicted pharmacology of the drug.

Due to the favorable tolerability profile of ganaxolone in Study 1042-0600 and its open-label extension, the current study is designed to further examine the safety, tolerability and efficacy in a second year of open-label treatment with ganaxolone when used as an add-on therapy in adult subjects with drug-resistant partial-onset (focal) seizures.

7. STUDY OBJECTIVES

7.1 Primary

To assess the safety and tolerability of adjunctive ganaxolone during two-year open-label treatment in adult subjects with drug-resistant partial-onset seizures.

7.2 Secondary

To assess efficacy of adjunctive ganaxolone during a two-year open-label treatment in adult subjects with drug-resistant partial-onset seizures.

8. INVESTIGATIONAL PLAN

8.1 Overall Study Design and Plan

Study 1042-0604 is an open-label extension of Study 1042-0603, providing a two-year adjunctive ganaxolone treatment (900-1800 mg/d) to adult subjects with epilepsy consisting of partial-onset seizure (POS). Subjects will enter the study at their current dose of ganaxolone from study 1042-0603. The dose of ganaxolone may be adjusted for tolerability and response.

8.2 Discussion of Study Design

This open-label protocol is designed to provide ganaxolone to adult subjects with epilepsy consisting of uncontrolled POS who are deriving significant benefit from current ganaxolone adjunctive therapy. Subjects who have completed all scheduled clinical study visits in the previous protocol 1042-0603 and have shown a minimum 35% improvement in mean seizure frequency per 28-days vs. baseline over the three 28-day periods preceding study entry, and acceptable tolerability, are eligible to participate. Safety and tolerability will be assessed by diary record and at clinic visits approximately every four months. During the study if the patient fails to continue to meet the minimum improvement criteria (mean 28-day seizure frequency over the past three 28-day periods before the study visit showing 35% improvement over baseline) at any study visit the investigator should consider discontinuing the patient from the study. Efficacy will primarily be assessed based on daily seizure calendar entries. Baseline for evaluation of seizure frequency will be each subject's baseline from Study 1042-0603, though other calculations may also be performed.

Adjunctive therapies (1-3 background AED medications, with or without implanted VNS) should be stable for the one month prior to study entry but may be adjusted as clinically warranted at other times during the study. The dose of ganaxolone may be adjusted as minimum 3 day intervals as warranted for tolerability and efficacy, up to a maximum of 1800 mg/d.

8.3 Selection of Study Population

8.3.1 Number of Subjects:

This study may treat up to approximately 350 subjects depending upon the number of subjects continuing from the previous Study 1042-0603.

8.3.2 Inclusion Criteria

1. Subjects who have completed all scheduled clinical study visits in the previous protocol 1042-0603 and have shown a minimum 35% improvement in mean 28-day seizure frequency over the last three 28-day periods in study 1042-0603 as compared to the baseline of study 1042-0603.
2. Subjects whose daily study drug compliance in Study 1042-0603 was 90% or greater, and for whom the investigator feels that the subject was compliant with the full dose as prescribed.
3. Able to give informed consent in writing, or have a legally authorized representative able to do so, after being properly informed of the nature and risks of the study and prior to engaging in any study-related procedures.
4. Currently being treated and maintained with a stable regimen of 1, 2, or 3 AEDs at a consistent dose for one month prior to study entry. See [Section 8.4.8](#) for restrictions on certain AEDs.
5. Implanted VNS (Vagus Nerve Stimulator) is permitted and will not count towards the number of concomitant AEDs.
6. Able and willing to maintain an accurate and complete daily written seizure calendar or has a caregiver who is able and willing to maintain an accurate and complete daily written seizure calendar.
7. Able and willing to take drug with food twice daily. Ganaxolone must be administered with food.
8. Sexually active women of childbearing potential (WCBP) must be using a medically acceptable method of birth control and have a negative pregnancy test at Visit 1 and at subsequent visits. A woman of childbearing potential is defined as a female who is biologically capable of becoming pregnant. A medically acceptable method of birth control includes intrauterine devices in place for at least 3 months, surgical sterilization, or adequate barrier methods (e.g., diaphragm and foam). An oral contraceptive alone is not considered adequate for the purpose of this study. Use of oral contraceptives in combination with another method (e.g., a spermicidal cream) is acceptable. In subjects who are not sexually active, abstinence is an acceptable form of birth control. Birth control should be continued for a minimum of 3 days after the last dose of study drug.

8.3.3 Exclusion Criteria

1. Have any medical condition that, in the investigator's judgment, is considered to be clinically significant and could potentially affect subject safety or study outcome, including but not limited to: clinically significant cardiac, renal, pulmonary, gastrointestinal, hematologic or hepatic conditions; or a condition that affects the absorption, distribution, metabolism or excretion of drugs.
2. Experienced a Serious Adverse Event or a moderate or severe medically important adverse event judged probably or definitely related to open-label ganaxolone in the previous study, 1042-0603.
3. Have Alanine transferase (ALT; SGPT) or Aspartate transferase (AST; SGOT) levels >3 times upper limits of normal (ULN), or total bilirubin >1.5 times ULN during Study 1042-0603. (Since Study 1042-0603 Visit 10 safety laboratory results will not be available at the time of inclusion in Study 1042-0604, these results will be assessed against [Section 8.3.4.Criterial for withdrawal #11.](#))
4. Have a history of malignancy within the past 2 years, with the exception of basal cell carcinoma.
5. Seizures secondary to illicit drug or alcohol use, infection, neoplasm, demyelinating disease, degenerative neurological disease, or central nervous system (CNS) disease deemed progressive, metabolic illness, or progressive degenerative disease.
6. Have active suicidal plan/intent, or have had active suicidal thoughts in the past 6 months. Have a history of an actual suicide attempt in the last 5 years or more than 1 lifetime actual suicide attempt as classified by the Columbia-Suicide Severity Rating Scale (C-SSRS).
7. Have a history of drug or alcohol abuse within the past 5 years. As with other AEDs, the use of alcohol is not advised.
8. Are currently following or planning to follow a ketogenic diet.
9. Current use of vigabatrin or ezogabine (retigabine; Potiga; Trobalt) is not permitted.
10. Females who are pregnant, currently breastfeeding or planning to become pregnant during the study.
11. Inability/unwillingness to withhold grapefruit and grapefruit juice from diet during the entire clinical trial.

Subjects meeting all inclusion and exclusion criteria will be allowed to enroll into this

study at the Investigator's discretion.

8.3.4 Removal of Subjects from Therapy or Assessments

8.3.4.1 Criteria for withdrawal

All subjects reserve the right to withdraw from the clinical study at any time, as stated in the informed consent form (ICF). The Investigator may discontinue subjects from the clinical study for any of the following reasons:

1. QTc interval >500 msec or uncorrected QT interval >600 msec; for subjects with bundle branch block, QTc >530 msec based on average QTc value of triplicate ECGs. A subject with an increase in QTc of >60 msec from Visit 1 must also be withdrawn.
 - a. If an ECG indicates a QTc interval outside of these limits, then 2 additional ECGs should be collected and the average QTc value of these 3 ECGs will be used. If the average values of the triplicate ECGs exceed the stated limits, the subject must be withdrawn.
2. Subject is found to have entered the clinical investigation in violation of the protocol;
3. Subject requires the use of an unacceptable or contraindicated concomitant medication. Should a prohibited CYP 3A 4, 5, 7 inhibitor or inducer be required for short term treatment, the subject may be permitted to remain in the study with permission from the Sponsor's Medical Monitor.
4. Use of benzodiazepines as rescue for innumerable seizure clusters more than three times in a 28-day period must be reviewed with Sponsor's Medical Monitor to assess suitability for continuation.
5. Subject's condition changes after entering the clinical investigation so that the subject no longer meets the inclusion criteria or develops any of the exclusion criteria;
6. Subject is noncompliant with procedures set forth in the protocol in an ongoing or repeated manner;
7. Subject experiences an adverse event (AE) that warrants withdrawal from the clinical investigation;
8. Patient's mean 28-day seizure rate over the past three 28-day periods before the study visit shows less than 35% improvement in comparison to the patient's baseline in the 1042-603 study;
9. It is the Investigator's opinion that it is not in the subject's best interest to continue in the study;

10. Any subject who exhibits any of the following will be immediately withdrawn from the clinical investigation:

- a. Clinically significant worsening of seizures as judged by Investigator or subject such that treatment outside of the protocol is assumed to be in the subject's best interest.
- b. Two episodes of generalized tonic-clonic seizures (GTCS) if not present in medical history.
- c. Status epilepticus at any time during the clinical investigation.
- d. Any Suicidal Behavior as classified by the Columbia Suicide Severity Rating Scale (C-SSRS) or a "yes" answer to questions 4 and 5 in the Suicidal Ideation section of the C-SSRS. These patients should be referred to psychiatric evaluation immediately.

11. Any subject who has the following liver enzyme findings should be immediately contacted and instructed to stop the study drug or start immediate down titration of the study drug

- a. ALT or AST $> 8 \times$ ULN
- b. ALT or AST $> 5 \times$ ULN for more than 2 weeks
- c. ALT or AST $> 3 \times$ ULN and total bilirubin $> 2 \times$ ULN
- d. ALT or AST $> 3 \times$ ULN with the appearance of fatigue, nausea, vomiting, right upper quadrant pain or tenderness, fever, rash or eosinophilia

Patients with ALT or AST $> 3 \times$ ULN but $\leq 8 \times$ ULN and no clinical signs or symptoms indicating liver dysfunction can, at the discretion of the investigator, continue the intake of study drug with close monitoring.

All patients who fall into either category (patients who must discontinue the study drug [a, b, c, and d] and who may continue the study drug with close monitoring) must be brought back to the study center without any delay, the next day if possible, but no later than 72 hours after the study results have been received, for evaluation of the underlying cause and confirmatory laboratory testing. More frequent monitoring of the liver tests should be initiated.

Discontinuation decisions will be made at each participating site by the Site Principal Investigator. If feasible, the process of discontinuation should be discussed with the Medical Monitor. The decisions regarding the discontinuation of the investigational therapy, whether the study medication should be stopped immediately or tapered should be discussed with the Medical Monitor, but final decisions about the process will remain at the discretion of the Site Principal Investigator.

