12.6 Appendix 6: Columbia Suicide Severity Rating Scale (C-SSRS) Since Last Visit

Translations in Bulgarian, German, Polish and Russian are available upon request.

COLUMBIA-SUICIDE SEVERITY RATING SCALE (C-SSRS)

Since Last Visit

Version 1/14/09

***Posner, K.; Brent, D.; Lucas, C.; Gould, M.; Stanley, B.; Brown, G.; Fisher, P.; Zelazny, J.;
Burke, A.; Oquendo, M.; Mann, J.***

Disclaimer:

This scale is intended for use by trained clinicians. The questions contained in the Columbia-Suicide Severity Rating Scale are suggested probes. Ultimately, the determination of the presence of suicidality depends on clinical judgment.

Definitions of behavioral suicidal events in this scale are based on those used in ***The Columbia Suicide History Form***, developed by [name] and [name], Conte Center for the Neuroscience of Mental Disorders (CCNMD), New York State Psychiatric Institute, [name]. (Oquendo M. A., Halberstam B. & Mann J. J., Risk factors for suicidal behavior: utility and limitations of research instruments. In M.B. First [Ed.] Standardized Evaluation in Clinical Practice, pp. 103 -130, 2003.)

For reprints of the C-SSRS contact [name]., New York State Psychiatric Institute, [name]; inquiries and training requirements contact [contact]

SUICIDAL IDEATION		Since Last Visit																		

Ask questions 1 and 2. If both are negative, proceed to "Suicidal Behavior" section. If the answer to question 2 is "yes," ask questions 3, 4 and 5. If the answer to question 1 and/or 2 is "yes", complete "Intensity of Ideation" section below.
 
1. Wish to be Dead Subject endorses thoughts about a wish to be dead or not alive anymore, or wish to fall asleep and not wake up. Have you wished you were dead or wished you could go to sleep and not wake up?
 
If yes, describe:
			
Yes  No 
																	

2. Non-Specific Active Suicidal Thoughts General, non-specific thoughts of wanting to end one's life/commit suicide (e.g. "I've thought about killing myself") without thoughts of ways to kill oneself/associated methods, intent, or plan during the assessment period. Have you actually had any thoughts of killing yourself?
 
If yes, describe:
		
Yes  No 
																		

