
3. Active Suicidal Ideation with Any Methods (Not Plan) without Intent to Act Subject endorses thoughts of suicide and has thought of at least one method during the assessment period. This is different than a specific plan with time, place or method details worked out (e.g. thought of method to kill self but not a specific plan). Includes person who would say, "I thought about taking an overdose but I never made a specific plan as to when, where or how I would actually do it....and I would never go through with it". Have you been thinking about how you might do this?
 
If yes, describe:
		
Yes  No 
																		

4. Active Suicidal Ideation with Some Intent to Act, without Specific Plan Active suicidal thoughts of killing oneself and subject reports having some intent to act on such thoughts, as opposed to "I have the thoughts but I definitely will not do anything about them". Have you had these thoughts and had some intention of acting on them?
 
If yes, describe:
		
Yes  No 
																		

5. Active Suicidal Ideation with Specific Plan and Intent Thoughts of killing oneself with details of plan fully or partially worked out and subject has some intent to carry it out. Have you started to work out or worked out the details of how to kill yourself? Do you intend to carry out that plan?
 
If yes, describe:
		
Yes  No 
																		
INTENSITY OF IDEATION																				

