		
appearance of fatigue, nausea, vomiting, right upper quadrant pain or tenderness, fever, rash or eosinophilia
 
Patients with ALT or AST .3xULN but <8xULN and no clinical signs or symptoms indicating liver dysfunction can, at the discretion of the investigator, continue the intake of study drug with close monitoring.
 
All patients who fall into either category (patients who must discontinue the study drug [a, b c, and d] and who may continue the study with close monitoring) must be brought back to the study center without any delay, the next day if possible, but no later than 72 hours after the study results have been received, for evaluation of the underlying cause and confirmatory laboratory testing. More frequent monitoring of the liver tests should be initiated.

--	--	--

Reason for Change: Subjects with <35% improvement in seizure frequency as compared to baseline: This criteria is intended to ensure that patients are periodically assessed for benefits and risks of ganaxolone, and that the patients who no longer derive significant benefit from ganaxolone are considered for exclusion. **C-SSRS:** More specific guidance how to utilize the C-SSRS instrument in assessing risk for suicide is provided. Specifically, patients with any suicidal behavior and/or suicidal ideation with intent or plan (ideation questions 4 and 5 in the C-SSRS) should be discontinued from the study and referred to psychiatric evaluation. **Managing elevated LFTs:** These stopping rules are intended to guide the investigator how to manage patients with elevated liver enzymes during the study. These stopping rules are in line with FDA's recommendation on managing patients with elevated liver enzymes during clinical trials (Guidance for Industry: Drug-Induced Liver Injury: Premarketing Clinical Evaluation)

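### Withdrawal item 10d joins C-SSRS ideation questions 4 and 5 with *and*: read literally, mandatory withdrawal and psychiatric referral follow only when both are yes, although Appendix 7 shows that either was meant to suffice (minor)

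*Protocol*

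**What the plan says.** Item 10 of protocol section 8.3.4.1 (Criteria for withdrawal) lists findings that require immediate withdrawal. Its sub-item d names any suicidal behavior on the C-SSRS, or a *yes* "answer to questions 4 and 5 in the Suicidal Ideation section of the C-SSRS". The next sentence sends these patients for immediate psychiatric evaluation.

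The form in Appendix 6 scores the two questions separately, each with its own yes/no box. Question 4 is headed "Active Suicidal Ideation with Some Intent to Act, without Specific Plan". Question 5 is described as "Thoughts of killing oneself with details of plan fully or partially worked out and subject has some intent to carry it out".

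Appendix 7 gives the sponsor's reason for the current wording of 10d: patients with "any suicidal behavior and/or suicidal ideation with intent or plan (ideation questions 4 and 5 in the C-SSRS) should be discontinued" and referred for psychiatric evaluation.

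The general list in 8.3.4.1 opens with what the investigator *may* do. It includes development of an exclusion criterion (item 5), an adverse event that warrants withdrawal (item 7) and the subject's best interest (item 9). Exclusion criterion 6 in section 8.3.3 begins "Have active suicidal plan/intent, or have had active suicidal thoughts in the past 6 months".

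**The concern.** The operative sentence uses *and* where the rationale for the same sentence uses *or*. A site that takes *and* as a joint condition would conclude that a subject with intent to act but no specific plan does not meet 10d. Withdrawal of that subject would then look optional, and the one psychiatric referral instruction in the available text would not apply, because it refers back to the patients caught by 10d.

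Safety and tolerability are the primary objective, and discontinuation is decided site by site, with approximately 58 sites planned in six countries. A mandatory suicidality rule in that setting should have one reading, and an investigator should not need a change-log rationale to find it.

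**Working it through.** No figure in the plan needs reproducing. The check enumerates the answer patterns, looks at how the protocol uses *and* nearby, and counts the visits at which the readings could differ.

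**1. Answer patterns.** Inputs: item 10d and the two separate yes/no items in Appendix 6, for a subject with no suicidal behavior.

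| Question 4 | Question 5 | Triggered if *and* is joint | Triggered if either suffices |
|---|---|---|---|
| no | no | no | no |
| yes | no | **no** | **yes** |
| no | yes | **no** | **yes** |
| yes | yes | yes | yes |

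The joint reading triggers on 1 of 4 patterns and the either-question reading on 3 of 4, so the readings differ on 3 − 1 = 2 patterns: question 4 only and question 5 only. These are counts of patterns, not probabilities. The question-5-only pattern is possible because question 4 is headed as ideation without a specific plan; a rater who applies that heading strictly could mark a subject with a plan *no* on 4 and *yes* on 5.

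**2. Which reading the text favours.**

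- For either question: Appendix 7 ("any suicidal behavior and/or suicidal ideation with intent or plan (ideation questions 4 and 5 in the C-SSRS) should be discontinued") explains wording that is still in force. Item 11 uses *and* in a list of separate triggers ("patients who must discontinue the study drug [a, b, c, and d"). Question 5 already includes intent, so requiring question 4 as well would add little.
- For a joint condition: item 11c uses *and* between two thresholds that must both be met ("ULN and total bilirubin"). The C-SSRS form writes *and/or* when either answer is enough ("If the answer to question 1 and/or 2 is"). Sentence 10d itself uses *or* between behavior and ideation, then switches to *and* between the two questions.

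The first group is the stronger, because it includes the sponsor's own explanation. None of it changes the words of 10d.

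**3. What covers the two patterns under the joint reading.** Item 5 (through exclusion 6), item 7 and item 9 each permit withdrawal. All three fall under *may*, and none carries a psychiatric referral. The reviewed copy lacks the protocol text between sections 9.5.2 and 9.5.3.3, so a referral instruction there cannot be ruled out.

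**4. Visits at stake.** The Schedule of Events (protocol Table 1) places the C-SSRS at Visits 2 to 8, which is 7 scheduled assessments after entry.

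- Visits 2, 3, 4, 5 and 6 (weeks 17, 34, 52, 69, 86): 5 assessments where withdrawal and referral can both differ.
- Visits 7 and 8 (weeks 104 and 106): 7 − 5 = 2 assessments where only the referral can differ, since the taper starts at Visit 7 in any case.

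**The case against.** The strongest reply is that the protocol already states its meaning. Appendix 7 belongs to the same document, explains this very phrase, and covers both withdrawal and referral for intent or plan. The joint reading also fits the scale poorly, and the evidence for it is thin: item 11c joins two laboratory thresholds inside one criterion, and the *and/or* comes from a third-party form. Subjects outside a literal 10d can still be withdrawn under items 5, 7 or 9. Section 8.3.4.2 returns discontinued subjects to their physician's care and follows unresolved adverse events. The form is meant for trained clinicians and leaves the determination to clinical judgment.

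Most of this stands, and it is why the point is minor. It does not make the operative sentence say *or*. A rationale in an amendment history does not amend the rule that sites apply, the other routes are discretionary, and return to usual care is not the immediate psychiatric referral that 10d requires.

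A reader might infer something stronger: that the protocol deliberately keeps subjects with suicidal intent on drug, or that the rule has been shown to miss them. The documents do not support that. Appendix 7 points the other way, exclusion 6 gives a route to withdrawal, and no affected subject can be identified. Nor is this a conflict between current and superseded text: the Appendix 7 sentence is the stated reason for the current wording.

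**Conclusion.** The point holds as a wording defect in a mandatory safety rule, of minor severity. Taken literally, item 10d covers one of four answer patterns where the sponsor's rationale implies three. The two omitted patterns rest on investigator discretion, with no psychiatric referral instruction in the text available.

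The conclusion assumes that the two questions are scored independently, as the form's layout allows, and that some site might read *and* as joint. How many subjects, if any, showed either pattern cannot be learned from the documents. SAP section 9 records early termination and low patient numbers, so the practical effect is probably small. No endpoint, population or analysis depends on it.

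**What to change.** In item 10d, replace *questions 4 and 5* with *question 4 or question 5*, so that a *yes* to either one triggers the rule. Leave the suicidal-behavior limb as it is, and keep the referral sentence so that it applies to either answer. If any subject remains on treatment, send sites a short notice of the clarified rule.

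The cost is one phrase in the protocol and, if needed, that notice. No new data and no SAP change are required. If no subject remains on treatment, the only benefit left is a correct protocol text.
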